CLINICAL PROTOCOL

**AQARESIS UTILITY FOR HYPONATREMIC ACUTE HEART FAILURE
(AQUA-AHF) STUDY**

Protocol #: HS-13-00705

Phase IV

Principal Investigators:

[name], Pharm.D.

[name].

Co-Investigators:

[name].

[name].

[name].

Study Site:

Los Angeles County + University of Southern California Medical Center

University of Southern California

Los Angeles, California

PI Contact Information:

[name], Pharm.D., FCCP, BCPS (AQ-C)

Associate Professor of Clinical Pharmacy and Medicine

University of Southern California School of Pharmacy

[name]

[name]

[contact]

[name] office

[contact] fax

Version: March 8, 2013

Amendment 1: July 30, 2014

Amendment 2: August 9, 2017

Protocol Synopsis

AQUARESIS UTILITY FOR HYPONATREMIC ACUTE HEART FAILURE (AQUA-AHF) STUDY Protocol # HS-13-00705	
Study Type	Prospective, randomized, open-label, parallel-group
Hypothesis	Volume management of acute congestive heart failure complicated by hyponatremia with a vasopressin-receptor antagonist-based aquaretic regimen is more effective and with fewer adverse events than a loop diuretic-based regimen.
Objectives	
 1. Compare urine output and length of hospital stay between a vasopressin receptor antagonist-based regimen to a loop diuretic-based regimen for hyponatremic heart failure patients hospitalized with evidence of volume overload. 2. Compare the safety (renal function, electrolyte abnormalities, and hemodynamics) of vasopressin receptor antagonist-based to a loop diuretic-based regimen for hyponatremic heart failure patients hospitalized with evidence of volume overload.
Interventions	
 1. Tolvaptan (with rescue loop diuretic or metolazone). 2. Furosemide (with rescue metolazone) 
Eligible patients will be randomized within 48 hours of presentation to the hospital. Tolvaptan will be dosed initially at 30mg daily, with the option to titrate up to a maximum of 60mg daily. Furosemide will be initiated as a continuous infusion at 5mg/h, with the option to titrate higher. Monotherapy with the study medication must be continued for at least the first 24 hours. If after 24 hours the diuretic response is deemed inadequate, the dose of study medication may be increased and/or the use of additional diuretic agents may be initiated at the discretion of the treating physician. Physicians will be encouraged to increase the primary study drug before the use of additional diuretic agents as clinically acceptable.

Patient Population	
N=50
 
Requiring hospitalization for acute heart failure with evidence of volume overload, and a serum sodium concentration of < 135 mEq/L documented within the first 48 hours of the admission. Initial treatment with diuretics prior to randomization is allowable. A maximum of 25 patients will be enrolled with serum sodium concentrations between 130 to 134 mEq/L as the inclusion.

Inclusion Criteria	
Acute HF with signs or symptoms of volume overload (i.e. elevated JVP, rales, edema)
 
Serum sodium < 135 mEq/L at time of or within first 48 hours of hospitalization
 
Randomized within 48 hours of presentation to hospital
 
≥ 18 years of age
 
Informed consent

Exclusion Criteria
	
Severe symptomatic hyponatremia requiring acute treatment (Patients requiring intervention to raise serum sodium urgently to prevent or to treat serious neurological symptoms e.g. any seizure activity or any neurologic impairment deemed to require immediate treatment by the primary treating physician) Severe renal impairment upon admission (creatinine clearance < 20 mL/min) Renal replacement therapy dependent, or requiring upon admission Acute coronary syndrome on admission Evidence of cardiogenic shock or requiring intravenous vasopressors VAD Pregnancy Patient requiring concomitant use of strong CYP3A4 inhibitors (clarithromycin, ketoconazole, itraconazole, ritonavir, indinavir, nelfinavir, saquinavir, nefazodone, and telithromycin)


Primary Endpoints
	
Primary efficacy endpoint: Mean urine output at 24 hours post randomization Primary safety endpoint: Mean change in serum creatinine at 24 hours post randomization

Secondary Endpoints
	
Efficacy: Urine output at 8, 48, 96 hours post-randomization, total at discharge Mean hourly urine output at 24 hours Serum sodium change at 8, 24, 48, 96 hours, and at discharge Weight change at 24, 48, 96 hours, and at discharge Cumulative furosemide dose at 48, 96 hours, and at discharge Cumulative use of metolazone at 48, 96 hours, and at discharge Self-rated change in dyspnea (Likert Scale) at 24 and 96 hours Safety: GFR change at 24, 48, 96 hours, and at discharge (estimated from Scr) Acute worsening of kidney function (increase in Scr 0.3 mg/dL or 25% above baseline) Electrolyte abnormalities (hypokalemia, hypomagnesemia, hyper/hyponatremia) Hypotension Changes in plasma renin activity, copeptin, cystatin C concentrations, NT-proBNP In-hospital mortality Hospital length of stay (ICU and total)

Statistical Plan
	
A total of 50 patients (25 in each group) would provide 93% power to detect a difference of 50% in urine output at 24 hours between treatments, alpha=0.05. The power was calculated based on the magnitude of difference in urine output seen in the ACTIV-CHF (24 hour mean urine output for tolvaptan was approximately 4100±2100mL vs 2300±1100mL compared to placebo when added to standard therapy) and in the Udelson et al study (24 hour mean increase in urine output with tolvaptan monotherapy 2600±1500mL vs 900±850mL with furosemide). Based on our previous data demonstrating poor response to loop diuretics in the hyponatremia acute HF population, we believe

	
a 50% difference (standard deviation of 25%) is a reasonable and conservative estimate of what the difference will likely be.
 
Descriptive statistics will be computed for each treatment group. For all comparative analyses between the two treatment groups, independent samples t-test and Chi-Square test (or Fisher’s exact test) will be performed for continuous variables or categorical variables, respectively. If either the normality or equal-variance assumptions underlying the traditional t-tests are violated, a non-parametric test will be used.
 
Amendment August 9, 2017: Due to slow enrollment, we anticipate not achieving our desired sample size of 50 subjects. Our revised power calculation reveals that if we achieve a mean difference with the same magnitude standard deviation between groups (e.g. mean difference is 1000±1000mL), our power will be between 80-90% with a sample size between 34-46 subjects. Based on current rate of enrollment, it is likely that we will achieve a sample of at least 34 subjects, which should allow the results to be meaningful despite early termination of enrollment.

Study Duration	18 months

Table of Contents

	Page
List of Abbreviations	6
1. Introduction	7
2. Study Rationale and Objectives	9
3. Study Design	

1.1 Hyponatremia in Hospitalized Patients

Hyponatremia is one of the most commonly encountered electrolyte abnormalities in hospitalized patients.¹⁻⁵ In clinical practice, hyponatremia is usually defined as serum sodium of ≤ 135 mmol/L (mEq/L). Although hyponatremia is commonplace in the hospitalized setting, the true incidence of this condition remains poorly characterized. Zilberberg and colleagues in a retrospective cohort study of over 190,000 patients reported a 5.5% incidence of hyponatremia at the point of hospital admission.⁶ However, other studies suggest that the incidence may be as high as 15%.¹

Extensive literature suggest that hyponatremia in the hospitalized setting is associated with an increase in mortality. Uncontrolled trials have reported mortality in hyponatremic patients ranging from 5-51% depending on study design and serum sodium cut-offs. One prospective observational, case controlled study found that mortality of hospitalized patients with hyponatremia was 27% compared to 9% in normonatremic patients.⁷ This study also found that patients with hyponatremia had higher serum creatinine concentrations and longer length of hospital stays as compared to controls. Zilberberg et. al. also found a higher in-hospital mortality rate in hyponatremic patients (5.9%) compared to normonatremic patients (3%).⁶ In addition, even mild hyponatremia (serum sodium concentration between 130-134 mEq/L) may be detrimental, increasing in-hospital mortality by 37% compared to those with normonatremia.² It remains unclear why hyponatremia is associated with increased mortality. It is hypothesized that hyponatremia may be a signal for important physiologic abnormalities in patients with cardiovascular diseases, or a predictor of other severe consequence associated with sodium irregularities such as cerebral edema.²

1.2 Hyponatremia and Heart Failure Outcomes

Heart failure (HF) patients are especially prone to developing hyponatremia. Several retrospective analyses have reported the prevalence of hyponatremia in the chronic HF population to be 19.7-27% based on admission serum sodium concentrations.⁸⁻¹² Heart failure patients often develop hypervolemic hyponatremia due to water retention which is associated with excessive neurohormonal stimulation.¹³ However, hyponatremia may also persist in HF patients who are euvolemic.

Hyponatremia is frequently regarded as a marker for the severity of HF. Several studies have suggested that hyponatremia in HF is associated with increased length of stay, morbidity, and mortality.⁸⁻¹² In the OPTIMIZE-HF registry, lower admission sodium (<135 mmol/L) was associated with higher in-hospital mortality (6.0% vs. 3.2%), longer length of stay (6.4 days vs. 5.5 days), and 60-90 day mortality (12.4% vs. 7.1%) compared to normal admission sodium. For each 3 mmol/L decrease in admission sodium below 140 mmol/L, the risk of in-hospital mortality was increased by 19.5% in patients with left ventricular systolic dysfunction (LVSD) and by 8.6% in patients with non-LVSD.⁹ Similarly, in the OPTIME-CHF trial, patients with the lowest baseline serum sodium (median < 134 mmol/L) experienced longer length of hospital stays, and higher in-hospital and 60-day mortality. Consistent with the results from OPTIMIZE-HF, each 3 mmol/L decrease in admission sodium values was associated with an 18% relative increase in the probability of death within 60 days.⁸ In a study of HF patients with preserved left ventricular ejection fraction, Rusinaru et. al. demonstrated hyponatremia was a powerful predictor of 7-year mortality.¹² One limitation of all the above studies was that the assessment of hyponatremia was made based solely on admission serum sodium concentrations. Results from the ESCAPE trial suggest that a significant proportion of normonatremic patients on admission also developed hyponatremia during the hospitalization. This study found a 15.9% incidence of acute hyponatremia, although the association

to patient outcomes was not assessed.¹¹ However, we recently demonstrated that acute hyponatremia has the same prognostic value as hyponatremia detected upon admission.¹⁴ There is now mounting evidence that hyponatremia is more than just a marker of disease severity. The ACTIV in CHF trial suggested that correction of hyponatremia was associated with a survival advantage. The 60-day mortality among patients with serum sodium levels that improved was 11.1% compared to 21.7% in those with persistent hyponatremia.¹⁰

1.3 Hyponatremia and Treatment Response

In addition to its prognostic value, hyponatremia may have importance during the acute management of HF i.e. influencing responses to treatment. One concern related to the pharmacologic management of acute HF is the development of hypotension. Data from ADHERE, a registry of acute HF patients, demonstrated that low systolic blood pressure is an independent predictor of in-hospital mortality.¹⁵ Hyponatremia may predispose patients to hypotension. In the OPTIME-CHF study, sustained hypotension defined as a low systolic blood pressure for > 30 minutes requiring intervention, was more common in patients within the lowest quartile of serum sodium (132-135 mEq/L).⁸ We also demonstrated that hyponatremia was associated with an increased risk of sustained hypotension in our acute HF patient population.¹⁴

Another major concern in the management of acute HF is diuretic resistance. Patients on chronic loop diuretic therapy may fail to respond to escalating doses of diuretics. One proposed mechanism is the routine use of diuretics, which promotes the excretion of sodium, leads to the development or exacerbation of hyponatremia.^{13,16} Decreased sodium delivery to the kidney as a result of the decreased plasma sodium concentration would stimulate the macula densa to release renin, thereby activating the renin-angiotensin-aldosterone system (RAAS). This increase in RAAS activation may lead to further vasoconstriction and water retention, essentially counteracting the desired diuretic effect. In support of this contention, we've recently shown that acute or chronic hyponatremia, especially <130 mEq/L, was associated with higher loop diuretic dose requirements and more frequent need for escalation of the diuretic regimen to achieve the same level of diuresis as normonatremic HF patients.¹⁴ Severity of hyponatremia was also associated with a greater than two-fold increase in the incidence of diuretic resistance, acute worsening renal function, sustained hypotension, increased length of stay, and in-hospital mortality. Our study results raised two important questions: 1) whether correction of hyponatremia can prevent or lower the risk of complications with conventional diuretics and 2) whether alternative treatments such as aquaretics (i.e. vasopressin receptor antagonists) represent a superior treatment modality for these patients.

1.4 Tolvaptan and Volume Management in Heart Failure

Aquaresis with tolvaptan represents a potentially advantageous approach to the management of volume overload in HF, especially in patients presenting with concomitant hyponatremia. Several prospective, randomized, controlled trials have clearly demonstrated the efficacy of tolvaptan for augmenting diuresis when administered in combination with furosemide for the management of congestive HF symptoms.¹⁷⁻²² In addition, tolvaptan was also associated with a favorable safety profile, devoid of significant effects on serum electrolytes and incidence of acutely worsening renal function. The potential for tolvaptan to be used as an alternative to furosemide was recently considered in a study by Udelson et al.²³ Eighty-three patients with stable NYHA FC II-III systolic HF and evidence of congestive symptoms were randomized to tolvaptan 30mg, furosemide 80mg, or the combination for 7 days. Tolvaptan was associated with a significantly greater daily urine output (approximately 1700mL/24h greater than furosemide monotherapy) and decrease in body weight compared to furosemide or the combination. Importantly, this study did not evaluate patients in an acute

decompensated state, included only systolic HF patients, did not allow titration of diuretic doses, and was limited to comparison with furosemide administered orally. Our data indicating poor outcomes with loop diuretics in hyponatremic acute HF patients, along with the Udelson study, suggest that tolvaptan may be a superior treatment modality for patients presenting in acute HF complicated by hyponatremia. These are clinically challenging patients to manage due to their poor response to loop diuretics and their propensity for adverse effects. Hence they represent an important niche for alternative diuretic strategies. Therefore, there is a **critical need to evaluate the role of tolvaptan monotherapy as a first-line option** for the treatment of these clinically complex patients. The purpose of the current study is to prospectively evaluate the comparative efficacy and safety of a tolvaptan-based diuretic regimen compared to conventional diuresis with a furosemide-based regimen on short-term clinical and treatment outcomes in hyponatremic acute HF patients.

2. Study Rationale and Objectives

Hyponatremia is the most common electrolyte abnormality in the hospital setting.^{1,3} Hyponatremia, based on admission values, has been associated with higher in-hospital mortality, 60-day mortality, longer length of hospital stay, and requirement for hospital readmissions.^{2,4,5} Similar findings are applicable to hospitalized HF patients as well.⁸⁻¹¹ However despite these associations, the importance of hyponatremia to influence acute treatment decisions in acute HF remains equivocal due to a lack of data. Importantly, we've recently shown that moderate to severe hyponatremia, especially <130 mEq/L, was associated with higher loop diuretic dose requirements and more frequent need for escalation of the diuretic regimen to achieve the same level of diuresis as normonatremic patients.¹⁴ Severity of hyponatremia was also associated with a greater than two-fold increase in the incidence of diuretic resistance, acute worsening renal function, sustained hypotension, increased length of stay, and in-hospital mortality. Our study results raised two important questions: 1) whether correction of hyponatremia can prevent or lower the risk of complications with conventional diuretics and 2) whether alternative treatments such as aquaretics (i.e. vasopressin receptor antagonists) represent a superior treatment modality for these patients? Data from small subgroups of hyponatremic patients in the EVEREST and ACTIV-CHF studies indicated that tolvaptan is effective at raising serum sodium and urine output in these patients.^{20,21} In addition, tolvaptan monotherapy was shown to exert a greater effect on urine volume and weight loss than a fixed dose of furosemide in stable NYHA FC II-III systolic HF patients.²³ However, these were not acutely decompensated patients, and a fixed dose of tolvaptan was being compared to fixed dose oral furosemide. Therefore, there is a **critical need to evaluate the role of aquaresis with tolvaptan as an acute treatment modality for acute HF complicated by hyponatremia**. These patients pose a particularly difficult challenge when attempting to gain effective diuresis with loop diuretics. The **purpose** of the current study is to prospectively evaluate the comparative efficacy and safety of a tolvaptan-based diuretic regimen compared to conventional diuresis with a furosemide-based regimen on short-term clinical and treatment outcomes in hyponatremic acute HF patients. Both reduced and preserved left ventricular systolic function patients will be studied.

The following are the study objectives:

1. Compare urine output and length of hospital stay between a vasopressin receptor antagonist-based regimen to a loop diuretic-based regimen for hyponatremic heart failure patients hospitalized with evidence of volume overload.
2. Compare the safety (renal function, electrolyte abnormalities, hemodynamics, neurohormonal activation) of vasopressin receptor antagonist-based to a loop diuretic-based regimen for hyponatremic heart failure patients hospitalized with evidence of volume overload.

[figure not shown]
3. Study Design

3.1 Trial Design

3.1.1 Design

This will be a prospective, open-label, parallel-group, randomized study comparing a tolvaptan-based aquaretic regimen to a conventional continuous infusion loop diuretic-based regimen of furosemide. The initial 24 hours of study treatment will compare tolvaptan monotherapy to furosemide monotherapy. After the initial 24 hours, treatment regimens may be altered to achieve desired clinical goals.

3.1.2 Study Procedures Overview

	≤48h	Randomization	8 hours	24 hours	48 hours	72 hours	96 hours	Discharge
Inclusion / Exclusion	X							
Vitals		X	X	X	X	X	X	X
Labs		X	X	X	X	X	X	X
Cystatin C		X		X			X	
PRA/copeptin /BNP		X		X			X	
UO		X	X	X	X	X	X	X
Weight		X		X	X	X	X	X
Furosemide dose eq.		X	X	X	X	X	X	X
Dyspnea scale				X				X

3.1.3 Study Duration

Study subject enrollment to occur over a 12-18 month period. Data analysis will occur simultaneously once the final subject has been discharged from the hospital since no long term follow-up is planned.

3.2 Study Endpoints

3.2.1 Efficacy Endpoints

Primary efficacy endpoint:

Mean urine output at 24 hours post randomization

Secondary efficacy endpoints:

Urine output at 8, 48, 96 hours post-randomization, total at discharge

Mean hourly urine output at 24 hours

Serum sodium change at 8, 24, 48, 96 hours, and at discharge

Weight change at 24, 48, 96 hours, and at discharge

Cumulative furosemide dose at 48, 96 hours, and at discharge

Cumulative use of metolazone at 48, 96 hours, and at discharge

Change in self-rated dyspnea (Likert Scale) at 24 and 96 hours

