3.4.2 Study Drugs

Study drugs (and scheduled in-patient medications) will be administered in an open-label fashion.

Patients randomized to tolvaptan will receive the study medication orally once daily. Tolvaptan tablets will be administered at 24 hour intervals, scheduled based on when the initial dose is received.

Patients randomized to furosemide will receive the medication as a continuous infusion. The loop diuretic furosemide will be prepared as per standard procedures of the hospital pharmacy for administration via continuous intravenous infusion.

After the initial 24 hour monotherapy period, escalation of the treatment regimen for either study arm will be either based on a minimum urine output < 100 mL/h or otherwise at the discretion of the primary treating physician to achieve clinical goals (e.g. relief of dyspnea, improvement in peripheral edema, resolution of jugular venous distention, improvement in pulmonary congestion based on chest radiograph, etc.). Patients randomized to furosemide will not be eligible to receive tolvaptan as a mode to treatment escalation. Tolvaptan dose will not be increased if serum sodium rises > 8 mEq/8 hours or >12 mEq/24h.

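### Cumulative metolazone use is a secondary efficacy endpoint, but the listed rescue agents differ by arm, so it does not measure need for rescue on a common basis

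*Combined protocol and SAP*

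**What the plan says.** Section 3.2.1 and the synopsis list "Cumulative use of metolazone at 48, 96 hours, and at discharge" among the secondary efficacy endpoints. The entry beside it is cumulative furosemide dose at the same time points.

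The Interventions row of the synopsis names the rescue for each arm: "Tolvaptan (with rescue loop diuretic or metolazone") and "Furosemide (with rescue metolazone"). Under the same row, if the response is judged inadequate after the first 24 hours, the study drug may be increased and/or "the use of additional diuretic agents may be initiated at the discretion of the treating physician". It adds a preference: "Physicians will be encouraged to increase the primary study drug before the use of additional diuretic agents as clinically acceptable". Tolvaptan starts at 30 mg daily, "with the option to titrate up to a maximum of 60mg daily". For furosemide the text is "Furosemide will be initiated as a continuous infusion at 5mg/h, with the option to titrate higher", and no upper limit is given.

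Section 3.4.2 adds one restriction on agents: "Patients randomized to furosemide will not be eligible to receive tolvaptan as a mode to treatment escalation". It also rules out raising the tolvaptan dose after a rapid rise in serum sodium. Section 6.2 applies an ordinary two-group test to every comparison and makes no provision for the different rescue options.

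**The concern.** As an efficacy endpoint, lower metolazone use will be read as a better response to the assigned drug. For that reading to hold, a patient whose response is inadequate must have the same route to metolazone in either arm. On the listed agents this is not so. A furosemide-arm patient who needs an add-on has metolazone as the only named option, whereas a tolvaptan-arm patient may receive a loop diuretic and never appear in the metolazone count. Two arms with the same need for rescue can therefore differ on this endpoint.

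No listed endpoint counts added diuretics in the same way in both arms. What is at stake is a secondary efficacy claim about the period after 24 hours, when the need for a second drug is direct evidence on whether the first was adequate.

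**Working it through.** The documents state no rescue rate, no mix of rescue agents and no expected metolazone use, so there is no figure of the plan's own to reproduce. The direction can be derived; the size can only be illustrated.

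**Step 1. Direction at equal need.** Let r be the proportion needing an add-on, the same in both arms. Let s be the share of tolvaptan-arm rescues given as a loop diuretic without metolazone. Take metolazone as the add-on in the furosemide arm, as listed.

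- Furosemide arm: metolazone use = r
- Tolvaptan arm: metolazone use = r(1-s)
- Difference = r - r(1-s) = r × s, in favour of tolvaptan, and zero only if s = 0

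If the endpoint is analysed as an amount, the direction is the same at equal dosing among users, because each rescue by loop diuretic alone contributes zero metolazone.

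**Step 2. Does the neighbouring endpoint correct it?** Cumulative furosemide dose records loop-diuretic rescue in the tolvaptan arm when the agent is furosemide. In the other arm furosemide is the assigned treatment. At the starting 5 mg/h it reaches 5 × 48 = 240 mg by 48 h and 5 × 96 = 480 mg by 96 h with no rescue at all. A between-arm comparison of that total does not isolate rescue either.

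**Step 3. Illustrative size.** Assumptions, none from the documents: the endpoint is treated as any metolazone, yes or no; need is r = 30% or 40% in both arms; and 20%, 50% or 80% of tolvaptan-arm rescues include metolazone (1-s). The group sizes are from section 6.1: 25 per arm as planned, and 17 and 23 per arm from the amended total of 34 to 46. The chance of a two-sided Fisher p ≤ 0.05 was found by full enumeration of both binomials.

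| Share with metolazone (1-s) | Furosemide v tolvaptan, r = 30% | Significant, 17-25 per arm | Furosemide v tolvaptan, r = 40% | Significant, 17-25 per arm |
|---|---|---|---|---|
| 20% | 30% v 6% | 31-49% | 40% v 8% | 47-68% |
| 50% | 30% v 15% | 10-15% | 40% v 20% | 14-23% |
| 80% | 30% v 24% | 3-4% | 40% v 32% | 4-5% |

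For reference, with 40% in both arms and s = 0, a significant result favouring tolvaptan occurs in 1.1% of trials at 17 per arm and 1.5% at 25.

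**Step 4. Unequal need.** If 20% of the furosemide arm and 40% of the tolvaptan arm needed an add-on, and half of the tolvaptan-arm rescues included metolazone, use would be 20% and 0.40 × 0.50 = 20%. The endpoint would then show no difference although the tolvaptan arm needed add-ons twice as often.

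**The case against.** The strongest reply is that equal add-on need is doubtful on the plan's own terms. Physicians are encouraged to raise the study drug first. Furosemide has no stated ceiling, tolvaptan stops at 60 mg, and a rapid sodium rise blocks a tolvaptan increase. The furosemide arm may therefore have more room to avoid an add-on, which pushes metolazone use the other way. This stands. A reader might infer from the rescue lists that a tolvaptan advantage is built into the design; the documents do not support that, because Step 4 shows the two effects can cancel and nothing in the text fixes their sizes.

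A second reply is that metolazone is not stated to be exclusive. Added agents are at the physician's discretion, and section 3.4.2 excludes only tolvaptan in the furosemide arm. This stands too: metolazone is the only rescue named for furosemide, not the only one allowed.

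Third, cumulative use reads most naturally as an amount, which section 6.2 would test with a t-test or a non-parametric test. The Fisher figures are therefore an illustration, not the operating characteristics of the planned analysis.

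Fourth, the trial compares regimens, and furosemide dose equivalents are collected from randomization to discharge (section 3.1.2), so loop-diuretic rescue is not hidden. That is fair as a description of treatment given. It does not make metolazone alone, or furosemide alone, a like-for-like measure of need for rescue.

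**Conclusion.** The concern holds in a limited form. As written, the endpoint does not measure need for rescue on a common basis: at equal need it favours tolvaptan by r × s, and no other listed endpoint corrects this. The result depends on some tolvaptan-arm rescues being a loop diuretic alone, which the synopsis permits.

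The size is unknown. Under the assumed yes/no illustration it runs from substantial (significant in 31-68% of trials when 20% of tolvaptan-arm rescues include metolazone) to small (3-5% when 80% do). If add-on need differs between arms, the net direction cannot be determined from the documents.

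The primary endpoint, 24-hour urine output, is measured during the monotherapy period, before rescue is allowed, and is unaffected. This is a matter of how one secondary endpoint is defined and interpreted.

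**What to change.** In section 3.2.1 and the synopsis, replace cumulative metolazone use as an efficacy endpoint with *any diuretic added to the assigned study drug after 24 h*, reported as the proportion of patients by 48 h and by 96 h. Define it identically in both arms. Do not count dose increases of the assigned drug: any step of an infusion with no stated ceiling would be set against a tolvaptan range of 30 to 60 mg, and the same wording would again measure different things. Report metolazone amount, furosemide amount and study-drug dose increases descriptively by arm.

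The cost is endpoint wording. Section 3.5 already has adjustments to the treatment regimen documented at 24, 48, 72 and 96 h, so no visit is added and care does not change. The remaining weakness is that the new endpoint still reflects open-label physician discretion and the different room to titrate each study drug. The report should say so when interpreting it.
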